9.4.1.2 Documenting Adverse Experiences

The PI is responsible to document all AEs that occur during the study. AEs should be documented as a single medical diagnosis. When this is not possible, AEs should be documented in terms of signs/symptoms observed by the PI or reported by the subject at each study visit. Each AE that appears to be independent of any prior event will be reported separately.

All AEs occurring after the subject signs the informed consent form through the last study visit must be reported, regardless of AE causality. All AEs, whether in response to a query, observed by the study site personnel, or reported spontaneously by the subject, will be recorded.

At each visit during the study, the subject will be assessed for the occurrence of new and ongoing AEs. The following data will be collected on all AEs and recorded on the appropriate CRF:

- Event name (diagnosis preferred, if unknown, record the signs/symptoms)
- Onset date and end date
- Maximum intensity (severity)
- Seriousness
- Action taken regarding study device
- Corrective treatment, if given

Clinical Trial Protocol ATM-2201	Version 2.0 28-Oct-2022	Confidential Page 16/25
-------------------------------------	----------------------------	----------------------------

- Outcome
- Investigator assessment of causality

9.4.1.3 Serious Adverse Events

All AEs will be assessed as either serious or non-serious.

An SAE is defined as any untoward medical occurrence that at any dose:

- Results in death
- Is immediately life threatening, (the term "life threatening" in the definition of "serious" refers to an event in which the subject is at risk of death at the time of the event; it does not refer to an event which hypothetically might have caused death if it were more severe)
- Requires inpatient hospitalization or prolongation of existing hospitalization (hospitalization for elective surgery for a baseline condition is not considered an AE)
- Results in persistent or significant disability/incapacity (permanent or substantial disruption of a person's ability to conduct normal life functions)
- Is a congenital anomaly/birth defect
- Is a medically important event that may not be immediately life threatening or result in death or hospitalization but may jeopardize the subject and may require medical or surgical intervention to prevent one of the above listed outcomes. Examples of such events include, but are not limited to, allergic bronchospasm requiring intensive treatment in an emergency room or at home; blood dyscrasias or convulsions that do not result in inpatient hospitalization.

Note: A spontaneous abortion will be considered an SAE and must be reported per Reporting of SAEs under Section 9.4.1.6.

9.4.1.4 Assessment of Severity

The severity assigned to an AE should be determined by the maximum severity of the AE. The categories described below should be used to estimate the severity of AEs:

- **Mild:** Transient or mild discomfort; no limitation in activity; no medical intervention/therapy required
- **Moderate:** Mild to moderate limitation in activity; some assistance may be needed; no or minimal medical intervention/therapy required
- **Severe:** Marked limitation in activity; some assistance usually required; medical intervention/therapy required; hospitalization or prolongation of current hospitalization possible; may be incapacitating or life threatening

9.4.1.5 Assessment of Causality

The PI should assess the relationship of the AE to the study device as either "Related" or "Not Related". The following should be considered when assessing AE causality:

- **Related:** There is at least a reasonable possibility that the AE/SAE is related to the study device. Reasonable possibility means that there is evidence to suggest a causal relationship between the study device and the AE.

Clinical Trial Protocol ATM-2201	Version 2.0 28-Oct-2022	Confidential Page 17/25
-------------------------------------	----------------------------	----------------------------

- **Not Related:** There is little or no reasonable possibility that the AE/SAE is related to the study device. This assessment implies that the AE/SAE has little or no temporal relationship to the study device and/or a more likely or certain alternative etiology exists.

9.4.1.6 Reporting of Serious Adverse Events

Adverse events classified as “serious” require expeditious handling and reporting to ethica CRO within 24 hours of investigational center notification.

All SAEs, whether related or unrelated to study device, must be immediately reported to the ethica CRO Clinical Project Manager (or designate) within 24 hours of the PI’s awareness of the event. All SAEs must be reported via confirmed facsimile or email transmission and must be submitted on a written SAE report form signed by the PI within 24 hours of the PI’s awareness of the event.

PIs should not wait to receive additional information to fully document the event before notifying ethica CRO of an SAE. If only limited information is initially available, follow-up reports are required. Additional relevant information such as hospital records and autopsy reports should be provided to the Sponsor as soon as they are available.

The PI should take all appropriate measures to ensure the safety of the subjects, notably he/she should follow a subject with an SAE until the event has resolved or the condition has stabilized. This may imply that follow-up will continue after the subject has left the study, and that additional investigations may be requested by the Sponsor. When an SAE persists at the end of the study, the PI will conduct follow-up contacts with the subject until the PI/Sponsor agree the event is satisfactorily resolved and/or stabilized.

9.4.1.7 Pregnancy

During the study, all female subjects of childbearing potential should be instructed to contact the PI immediately if they suspect they might be pregnant (e.g., missed or late menstrual period).

If a subject or PI suspects that the subject may be pregnant prior to study enrolment, the study device must be withheld until the results of laboratory pregnancy testing are available. If pregnancy is confirmed, the subject must not receive study device and must not be enrolled in the study.

If pregnancy is suspected while the subject is receiving study device, the study device must immediately be withheld until the result of pregnancy testing is known. If pregnancy is confirmed, the study device will be permanently discontinued, and the subject will be followed until the pregnancy comes to term.

All confirmed pregnancies must be reported via confirmed facsimile or email transmission and must be submitted on an Unanticipated Problems Reporting Form within 24 hours of the PI’s awareness of the pregnancy using the same reporting as procedure for an SAE under Section 9.4.1.6.

10 STATISTICS

There is no inferential statistical testing conducted for this study. Descriptive data summaries will be prepared for all outcome variables.

For categorical parameters, the number and percentage of subjects/observations in each category will be presented. The denominator will be based on the number of subjects/observations appropriate for the purpose of analysis. For continuous parameters, descriptive statistics will

Clinical Trial Protocol ATM-2201	Version 2.0 28-Oct-2022	Confidential Page 18/25
-------------------------------------	----------------------------	----------------------------

include n (number of subjects or observations), mean, standard deviation, median, and range. Two-sided 95% CIs will be provided for all study outcomes.

10.1 Sample Size Determination

Approximately 20 subjects will be enrolled. This is a POC study and a formal sample size justification is not provided for this study. It is the opinion of the Sponsor that a total of 20 subjects will be sufficient to achieve the objective of the study.

10.2 Assessment of Safety

10.2.1 Adverse Events

All AEs occurring during the study will be recorded and classified on the basis of MedDRA terminology. Descriptions of AEs will include the date of onset, the date the AE ended, the severity of the AE, the relationship to study medication, the action taken regarding study medication usage, the action taken to treat the AE, and the outcome. All reported treatment-emergent AEs (TEAEs) and treatment-related events (TRAEs) will be summarized by the number of Subjects reporting AEs, system organ class, severity, seriousness, and relationship to study medication.

AEs will be summarized by treatment group and severity, and by treatment group and relationship to study device. Each subject will be counted only once within a system organ class or a preferred term by using the AEs with the greatest relationship within each category.

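### The single adverse event counting rule in Section 10.2.1 selects on relationship, so the severity table can understate a subject's worst severity

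*Combined protocol and SAP*

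**What the plan says.** Section 10.2.1 of the combined protocol and SAP sets out two tabulations in one sentence: "AEs will be summarized by treatment group and severity, and by treatment group and relationship to study device". The next sentence gives the only subject-level counting rule in the documents, under which a subject is "counted only once within a system organ class or a preferred term by using the AEs with the greatest relationship within each category". The same section also summarises treatment-emergent and treatment-related events by severity, among other attributes.

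Two other places mention maximum severity. Section 9.4.1.4 states: "The severity assigned to an AE should be determined by the maximum severity of the AE". Section 9.4.1.2 has the maximum intensity of each event recorded on the CRF. Both grade a single event.

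The wording of Section 10.2.1 also differs from what is collected. It describes "the relationship to study medication, the action taken regarding study medication usage", whereas Section 9.4.1.2 collects "Action taken regarding study device" and Section 9.4.1.5 defines causality for the device only: "The PI should assess the relationship of the AE to the study device as either" Related or Not Related.

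**The concern.** A table by severity should place each subject at the worst severity that the subject had in that SOC or PT. A rule that first picks the most related event can place the subject lower. It can never place the subject higher, because the selected event is always one of the subject's own.

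There are two ways for this to go wrong:

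1. The more severe of two events is the less related one. The rule then selects the milder event.
2. The two events have the same relationship and different severity. No tie-break is given, so the result depends on whoever programs the table. Both events may be device-related.

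The synopsis lists AEs as the only safety endpoint, and Section 2 makes safety of the adapter the sole objective, so these tables are the main output of the study. More than one event per subject in a SOC or PT is possible: up to three lesions are injected (Section 8.2) and independent events are reported separately (Section 9.4.1.2). The protocol does not say whether reactions at different lesions are separate events.

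**Working it through.** The plan gives no figure of its own on this point, so there is nothing to reproduce. The check applies the written rule to every case that it can meet with two events.

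**Inputs**
- Severity: 3 grades, mild, moderate and severe (Section 9.4.1.4).
- Causality: 2 levels, Related and Not Related (Section 9.4.1.5).
- Rule: take the event with the greatest relationship (Section 10.2.1).
- Sample size: about 20 (Section 10.1); 20 is used below.

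**Step 1. Patterns for one subject with two events in one SOC or PT**

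There are 3 × 2 = 6 event types, so 6 × 6 = 36 ordered pairs.

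| Situation | Count | Severity selected |
|---|---|---|
| Equal severity | 3 × 4 = 12 | Correct, whichever event is taken |
| Different severity, the more severe event is the Related one | 6 | Correct |
| Different severity, the less severe event is the Related one | 6 | Understated |
| Different severity, same relationship | 6 × 2 = 12 | Undetermined |
| Total | 36 | |

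So 12 + 6 = 18 are correct, 6 are certainly understated and 12 are undetermined. The 6 understated pairs are three combinations in either order:
- Related mild with Not Related moderate
- Related mild with Not Related severe
- Related moderate with Not Related severe

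Of the 12 undetermined pairs, 6 have both events Related and 6 have both Not Related. Depending on the tie-break, the number understated lies between 6 and 6 + 12 = 18.

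**Step 2. The treatment-related summary**

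If treatment-related means assessed as Related, every event in this summary has the same relationship and the rule cannot discriminate. Of the 3 × 3 = 9 ordered severity pairs, 3 have equal severity and 6 are undetermined.

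**Step 3. Size of one misplaced subject**

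One subject is 1/20 = 5 percentage points in a row. Section 10 says "Two-sided 95% CIs will be provided for all study outcomes" but names no method, so two methods are shown as an assumption.

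| Severe count in the row | Exact (Clopper-Pearson) 95% CI | Wilson 95% CI |
|---|---|---|
| 1/20 (true worst severity) | 0.1% to 24.9% | 0.9% to 23.6% |
| 0/20 (as tabulated) | 0% to 16.8% | 0% to 16.1% |

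For example, the exact upper limit for 0/20 is 1 − 0.025^(1/20) = 0.168, and the exact lower limit for 1/20 is 1 − 0.975^(1/20) = 0.0013.

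**Step 4. The same cases under a maximum-severity rule**

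All 36 pairs go to the worst severity, with none understated and none undetermined. The relationship table is unchanged.

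**The case against.** Five points can be made for the plan.

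- **The counting sentence may be meant for the relationship table only.** It follows the mention of relationship and selects on relationship, so this is a fair guess at intent. The text does not say so, and on that reading the severity table has no counting rule at all. Reading the closing words of the sentence as within each severity grade would let a subject appear in several grades, which conflicts with counting once per SOC or PT. Each reading still needs a text change.
- **Certain understatement cannot hide a device-related event.** This stands: in all 6 such patterns the more severe event is Not Related. The connection to device-related harm comes only through ties.
- **A tie is undetermined, not understated.** This also stands. Nothing in the plan directs the milder event to be chosen; 6 of 36 follows from the written rule, and 18 of 36 requires the least favourable tie-break every time.
- **The situation will be rare.** Probably so. It needs two or more events of different severity in one SOC or PT in one subject, after one injection session and 14 days of follow-up, with lesion pain and injection-site pain not counted as AEs (Sections 9.3.1 and 9.3.2).
- **Nothing is lost.** Each event's severity and seriousness are recorded, serious events are reported separately, and no hypothesis is tested. A correct table can be built at any time. That limits the harm, but choosing the rule after the events have been seen is worth avoiding when it can be fixed beforehand.

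**Conclusion.** The concern holds. Followed as written, Section 10.2.1 applies a relationship-based selector to the severity table, which understates worst severity in some cases and leaves it undefined in others. Sections 9.4.1.2 and 9.4.1.4 do not repair this, because they grade one event and do not choose among several.

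The pattern counts in the working describe which cases the rule mishandles, not how often they will arise. The documents give no AE rate, so no expected number of affected subjects can be stated, and it may be zero. The error only runs downward and is confined to subject-level counts in the severity tabulations. The interval comparison illustrates a single row at N = 20 and rests on an assumed CI method.

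This is a table-specification defect with no bearing on sample size or error rates. It should be corrected because the difference between one severe case and none matters in a study whose only objective is safety. The mismatch between medication and device wording is a minor point that should be reconciled; the conclusion does not depend on it.

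**What to change.** Replace the last sentence of Section 10.2.1 with text to this effect:

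> In tables by severity, each subject is counted once per SOC and once per PT, at the maximum severity. In tables by relationship, each subject is counted once per SOC and once per PT, at the strongest relationship to the study device.

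This also removes the tie problem, including in the treatment-related summary. In the same section, change the references to study medication to study device, so that treatment-related events are those assessed as Related under Section 9.4.1.5.

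The cost is a wording change through the route in Section 3.1. It needs no new data, CRF field or causality assessment. The only downside is that the severity table may look slightly less favourable.

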10.3 Analysis Populations

10.3.1 Intent-to-Treat (ITT) Population

The modified Intent-to-Treat (mITT) Population is defined as all subjects who were enrolled and received at least one application with the study device. The mITT Population will be used for analyses of safety and effectiveness endpoints.

10.3.2 Per-Protocol (PP) Population

A Per-Protocol (PP) Population will neither be defined nor analyzed.

10.3.3 Subject Disposition

A tabulation of subject disposition will be provided which will include the numbers of subjects who enter, complete, and discontinue the study. The reasons for discontinuation will be included.

10.3.4 Protocol Deviations and Violations

All protocol deviations and violations will be reported to the Sponsor and recorded throughout the study. A tabulation of protocol deviations will be included in the final study report.

10.3.5 Multicenter Issues

Not applicable

10.3.6 Missing Data Imputations

Data will be analyzed as observed; no imputations will be made for missing data.

10.3.7 Statistical Hypothesis Testing and Control of Multiplicity

Not Applicable.

Clinical Trial Protocol ATM-2201	Version 2.0 28-Oct-2022	Confidential Page 19/25
-------------------------------------	----------------------------	----------------------------

10.4 Interim Analyses

No interim analyses are planned.

11 QUALITY CONTROL AND QUALITY ASSURANCE

11.1 Study Monitoring

An initiation webinar will be conducted with the PI and study coordinator(s) by Sponsor and/or its designee. During this meeting, an extensive review and discussion of the protocol, all study procedures, source documents, and CRFs will be conducted. Evaluation scales will be reviewed extensively.

The Clinical Project Manager(s) and Clinical Trial Associate(s) will be trained prior to study initiation.

The conduct of the study will be closely monitored by the Sponsor (or designate) following GCP guidelines. The reports of these verifications will also be archived with the study report. In addition, inspections or on-site audits may be carried out by local and/or federal authorities. The PIs will allow the Sponsor's representatives and any regulatory agency to examine all study records, corresponding subject medical records, clinical dispensing records and storage area, and any other documents considered source documentation. The PIs agree to assist the representative, if required.

11.2 Audits and Inspections

The study will be conducted under the Sponsorship of the Sponsor in conformation with all appropriate local and federal regulations, as well as ICH guidelines.

11.3 Protocol Deviations

The PIs must read the protocol thoroughly and must follow the instructions exactly.

A deviation from the protocol is an unintended and/or unanticipated departure from the procedures and/or processes approved by the Sponsor and the IRB and agreed to by the PI. Deviations usually have an impact on individual subjects or a small group of subjects and do not involve inclusion/exclusion or tolerability and cosmetic endpoint criteria.

A protocol violation occurs when there is non-adherence to the protocol that results in a significant, additional risk to the subject, when the subject or PI has failed to adhere to significant protocol requirements (inclusion/exclusion criteria) and the subject was enrolled without prior Sponsor approval, or when there is non-adherence to ICH GCP guidelines.

The issue of noncompliance may be either on the part of the subject, the PI, or the study site staff. As a result of deviations, corrective actions are to be developed by the site and implemented promptly.

All protocol deviations and violations must be addressed in study subject source documents. A completed copy of the ethica CRO Inc. Protocol Deviation Form must be maintained in the regulatory file, as well as in the subject's source document. Protocol deviations must be sent to the IRB per its guidelines.

Clinical Trial Protocol ATM-2201	Version 2.0 28-Oct-2022	Confidential Page 20/25
-------------------------------------	----------------------------	----------------------------

12 ETHICS AND ADMINISTRATIVE ISSUES

12.1 Ethical Conduct of the Study

This study will be conducted in accordance with the ethical principles originating from the Declaration of Helsinki, ICH guidelines, GCP, and in compliance with local regulatory requirements. The PI agrees, when signing the protocol, to adhere to the instructions and procedures described in it and thereby to adhere to the principles of GCP.

12.2 Ethics Review

The study protocol, informed consent form and other information to subjects, and all appropriate amendments will be reviewed and approved by an Institutional Review Board (IRB). A signed and dated notification of the IRB approval will be provided to the Sponsor and PI prior to study initiation. The name and occupation of the chairman and members of the IRB will be supplied to the Sponsor to the extent allowable by the IRB. The PI will provide required progress reports and report all SAEs to the IRB as required by the IRB.

12.3 Written Informed Consent

This study will be conducted in compliance with 21 CFR Part 50 for informed consent.

The study coordinator will obtain written informed consent from each subject before any procedures or assessments are done and after the aims, methods, anticipated benefits, potential hazards, compensation and/or honoraria, and insurance arrangements in force are explained. It will also be explained to the subject that they are free to refuse entry into the study and free to withdraw from the study at any time without prejudice to future treatment. The Investigator will be available to respond as needed to questions raised by the participant.

Written and/or oral information about the study in a language understandable by the subject will be given to all subjects. The subjects will be given the opportunity to discuss the procedure, risks, benefits, alternative therapies and the study requirements with the Investigator (or qualified designee) and have any and all questions answered to the subject's satisfaction.

The subject's willingness to participate in the study will be documented in writing on a consent form, which will be signed by the subject with the date and time of that signature indicated.

The site will keep the original consent forms and copies will be given to the subjects.

12.4 Subject Data Protections

Subject data will be protected by ensuring that no captured data contain subject names, addresses, telephone numbers, email addresses, or other personally identifying information. It is acknowledged that subject initials, demographics (including birthdates), medical histories, and prior concomitant medication uses, along with the name and address of the enrolling PI may allow for personal identification of study participants. Other than where necessary to meet regulatory requirements, all data collected in this study will be presented in tabulated (i.e., aggregate) form and listings containing information that could be used to identify an individual subject will not be included in any public disclosures of the study data or the study results.

As part of the study database, study data will be stored at Equinix and Amazon Web Services facilities in Germany and Ireland that are SOC 1, SOC 2, ISO 27001, and FISMA examined and certified. Security monitoring includes biometric scanning protocols, continuous surveillance, and

Clinical Trial Protocol ATM-2201	Version 2.0 28-Oct-2022	Confidential Page 21/25
-------------------------------------	----------------------------	----------------------------

24x7 production environment management. Data privacy complies with Canadian and US standards, as well as the European Union's [General Data Protection Regulation \(GDPR\)](#).

The study database utilizes encryption to safeguard data and all data is durably stored with National Institute of Standards and Technology (NIST) approved ciphers, transport layer security (TLS) technology, and AES 256-bit at-rest encryption.

